6.2 Ancillary treatments

Any additional therapy used to treat NTD during this trial (e.g. therapy with hydroxyurea, erythropoietin, butyrate) will be permitted. Except for the study medication, no other iron chelation therapy will be administered while the patient is enrolled in the trial.

6.3 Concomitant medications

Use of the following treatments is NOT allowed after the start of study drug:

- Other investigational drugs
- Aluminum containing antacid therapies should be avoided because they may bind to deferasirox
- The concomitant use of deferasirox with potent UGT inducers (e.g. rifampicin, phenytoin, phenobarbital, ritonavir) may result in a decrease in deferasirox efficacy.
- The concomitant use of deferasirox with bile acid sequestrants (e.g., cholestyramine, colesevelam, colestipol) may result in a decrease in deferasirox efficacy.
- The use of hormonal contraceptives (oral or injected) is prohibited in this study due to a decrease in efficacy when used in combination with deferasirox.
- Any iron chelation therapy other than the study drug

Caution must be exercised in patients who are taking study drug in combination with the following drugs:

- The concomitant administration of deferasirox and vitamin C has not been formally studied. Doses of vitamin C up to 200 mg/days have not been associated with adverse consequences.
- Concomitant administration of deferasirox with drugs that have known ulcerogenic potential, such as NSAIDs, corticosteroids, or oral bisphosphonates, and use of deferasirox in patients receiving anticoagulants may increase the risk of gastrointestinal irritation and bleeding.
- Deferasirox, as a weak CYP3A4 inducer, may potentially decrease serum levels of substances metabolised through CYP3A4 (e.g. cyclosporin, simvastatin, hormonal contraceptive agents)
- Deferasirox is a moderate inhibitor of CYP2C8 and therefore it may increase serum concentrations of substances metabolised through CYP2C8 (e.g repaglinide, paclitaxel)
- Concomitant administration of deferasirox with CYP1A2 substrates that have a narrow therapeutic index (e.g. theophylline, clozapine, tizanidine), is not recommended. When deferasirox and theophylline are used concomitantly, monitoring of theophylline concentration and theophylline dose reduction should be considered.

A sporadic transfusion depending on the patient's condition (e.g. in case of infection) during the course of the study is allowed and will be recorded in the Transfusions eCRF.

The investigator must instruct the patient to notify the study site about any new medications (including over-the-counter products) he/she takes after the start of the study drug. All medications (other than study drug) and significant non-drug therapies (including physical therapy and blood transfusions) administered after the patient starts treatment with study drug must be listed on the Concomitant medications/Significant non-drug therapies after start of study drug eCRF.

6.4 Guidelines for continuation of treatment

For patients who are unable to tolerate the protocol-specified dosing schedule, dose adjustments are permitted in order to keep the patient on study drug. These changes must be recorded on the dosage administration record eCRF.

The majority of dose adjustments are covered in [Section 6.4.1](#) to [Section 6.4.11](#), below. For all cases where a dose adjustment is considered necessary but is not covered in the following sections, the investigator will send a written request to Novartis. The request must justify the dose change and provide all the supportive clinical and laboratory information for complete evaluation by Novartis. Any dose adjustment for reasons not included in this section needs to be authorized by Novartis. A written reply will be promptly sent back to the investigator by Novartis.

6.4.1 Change in patient weight

The dose of study drug will be adapted using [Table 6-1](#) through to [Table 6-6](#) according to the patient's body weight throughout the course of the study.

6.4.2 Change in serum ferritin

If the serum ferritin level decreases to < 300 ng/mL at any visit, study drug will be held and the LIC will be assessed by R2 MRI. If repeat serum ferritin is < 300 ng/mL, treatment with the study drug will be interrupted. Repeat serum ferritin may be done locally, within two weeks of scheduled visit. If LIC is ≥ 5 mg Fe/g dw and repeat serum ferritin is ≥ 300 ng/mL, study drug treatment will be restarted at the same dose. Study drug will be held until LIC is ≥ 5 mg Fe/g dw and serum ferritin is ≥ 300 ng/mL. Study drug treatment will be restarted at the same dose (maximum restart dose of 10 mg/kg/day). The investigator will record this change on the dosage administration record eCRF and will notify Novartis at the time such a dose interruption is made, in order to facilitate optimal safety monitoring.

6.4.3 Change in liver iron content (LIC) as determined by liver MRI

See [Section 6.1.1](#) Dosing regimen.

6.4.4 Serum creatinine and Creatinine clearance

Serum creatinine and creatinine clearance will be assessed at Weeks -4 and -2 before initiating therapy and should be monitored during the study as indicated in [Table 7-2](#).

During the treatment period, patients who develop an increase in serum creatinine $\geq 33\%$ above their baseline value (average of visit 1 and 2) resulting in a serum creatinine above the

upper limit of normal, on two consecutive occasions, the dose of the study drug will be reduced to:

- 15 mg/kg if the patient takes 30 mg/kg/day,
- 10 mg/kg if the patient takes 15-20 mg/kg/day,
- 5 mg/kg if patient takes 10 mg/kg/day,
- study drug held if patient takes 5 mg/kg/day of deferasirox

until serum creatinine returns to below the ULN.

In case of a single increase in serum creatinine, the assessment will be repeated in 2 weeks.

If after a dose reduction, a progressive increase in serum creatinine beyond the ULN is observed, a treatment interruption is recommended.

After an interruption, if serum creatinine falls below the age appropriate upper limit of normal range on two consecutive visits, it is recommended to resume therapy at 5 mg/kg/day, and after 1 month, if the serum creatinine increase does not recur, study medication can be doubled at one month intervals in order to return to the initial dose.

Caution should especially be used in patients with creatinine clearance between 40 and less than 60 mL/min, particularly in cases where there are additional risk factors that may impair renal function such as concomitant medications, dehydration, or severe infections.

Deferasirox therapy should be discontinued in case serum creatinine increases > 2 times the age-appropriate ULN or if creatinine clearance decreases < 40 mL/min.

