6.1.1 Dosing regimen

The starting dose of deferasirox for all patients will be 10 mg/kg/day for 4 weeks.

- After 4 weeks, the dose of deferasirox will be adjusted according to baseline LIC measurements:
 - 20 mg/kg/day for patients with baseline LIC > 15 mg Fe/g dw
 - 15 mg/kg/day for patients with baseline LIC > 7 but ≤ 15 mg Fe/g dw
 - Dose will remain at 10 mg/kg/day for patients with baseline LIC ≥ 5 but ≤ 7 mg Fe/g dw

- Approximately every 6 months (starting at Week 24), the dose of deferasirox will be further adjusted, according to the following LIC measurements:
 - Increase dose by 5-10 mg/kg/day if LIC is > 15 mg Fe/g dw, maximum of 30 mg/kg/day
 - May increase dose by 5 mg/kg/day if LIC is > 7 but ≤ 15 mg Fe/g dw, maximum of 20 mg/kg/day. Same dose if LIC is ≥ 3 but ≤ 7 mg Fe/g dw, maximum of 10 mg/kg/day

Patients who have been dose escalated will be monitored every week for four weeks after the escalation, to assess serum creatinine. Serum transaminases, bilirubin, and alkaline phosphatase will be assessed two weeks following dose escalation. This may be conducted at the local lab. After these periods (if they are applicable), the patient will visit the study center according to the monthly visit schedule.

If LIC measurement is < 3 mg Fe/g dw or SF is < 300 ng/mL, treatment will be interrupted. Patients will continue with visits during the period of treatment interruption and study treatment will restart at the previous effective dose when LIC ≥ 5 mg Fe/g dw and SF is ≥ 300 ng/mL (maximum of 10 mg/kg/day).

Dose adjustments based on safety issues are allowed in the study at any time. Investigator can reduce or interrupt study treatment and recommendations for such dose adjustments are described in [Section 6.4](#).

The maximum dose of deferasirox throughout the study will be 30 mg/kg/day.

Study Drug Administration

The patient will be instructed how to prepare his/her daily dose from the three tablet strengths of deferasirox [ICL670, Exjade[®]] available (125 mg, 250 mg, 500 mg). The dose will be assigned based on the patient's weight (see [Table 6-1](#) through to [Table 6-6](#)). Given the available strengths of deferasirox tablets, the patient's daily dose will be rounded to the nearest whole tablet size (relative to a 125 mg tablet).

Each time study medication is dispensed to the patient and/or the legal guardian, the investigator will provide detailed instructions on how to prepare and administer deferasirox.

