| Pt Weight in Kg | Closest dose | 125 mg | 250 mg | 500 mg |
|-----------------|--------------|--------|--------|--------|
| 20.0 - 21.9 | 375 | 3 | | |
| 22.0 - 28.1 | 500 | | | 1 |
| 28.2 - 34.4 | 625 | 1 | | 1 |
| 34.5 - 40.6 | 750 | | 1 | 1 |
| 40.7 - 46.9 | 875 | 3 | | 1 |
| 47.0 - 53.1 | 1000 | | | 2 |
| 53.2 - 59.4 | 1125 | 1 | | 2 |
| 59.5 - 65.6 | 1250 | | 1 | 2 |
| 65.7 - 71.9 | 1375 | 3 | | 2 |
| 72.0 - 78.1 | 1500 | | | 3 |
| 78.2 - 84.4 | 1625 | 1 | | 3 |
| 84.5 - 90.6 | 1750 | | 1 | 3 |
| 90.7 - 96.9 | 1875 | 3 | | 3 |
| 97.0 - 103.1 | 2000 | | | 4 |
| 103.2 - 109.4 | 2125 | 1 | | 4 |
| 109.5 - 115.6 | 2250 | | 1 | 4 |
| 115.7 - 121.9 | 2375 | 3 | | 4 |

[figure not shown]

Table 6-5 Deferasirox dosing table for 25 mg/kg/day

| Pt Weight in Kg | Closest dose | 125 mg | 250 mg | 500 mg |
|-----------------|--------------|--------|--------|--------|
| 20.0 - 22.5 | 500 | | | 1 |
| 22.6 - 27.5 | 625 | 1 | | 1 |
| 27.6 - 32.5 | 750 | | 2 | 1 |
| 32.6 - 37.5 | 875 | 3 | | 1 |
| 37.6 - 42.5 | 1000 | | | 2 |
| 42.6 - 47.5 | 1125 | 1 | | 2 |
| 47.6 - 52.5 | 1250 | | 1 | 2 |
| 52.6 - 57.5 | 1375 | 3 | | 2 |
| 57.6 - 62.5 | 1500 | | | 3 |
| 62.6 - 67.5 | 1625 | 1 | | 3 |
| 67.6 - 72.5 | 1750 | | 1 | 3 |
| 72.6 - 77.5 | 1875 | 3 | | 3 |
| 77.6 - 82.5 | 2000 | | | 4 |
| 82.6 - 87.5 | 2125 | 1 | | 4 |
| 87.6 - 92.5 | 2250 | | 1 | 4 |
| 92.6 - 97.5 | 2375 | 3 | | 4 |
| 97.6 - 102.5 | 2500 | | | 5 |
| 102.6 - 107.5 | 2625 | 1 | | 5 |
| 107.6 - 112.5 | 2750 | | 1 | 5 |
| 112.6 - 117.5 | 2875 | 3 | | 5 |
| 117.6 - 122.5 | 3000 | | | 6 |

Table 6-6 Deferasirox dosing table for 30 mg/kg/day

| Pt Weight in Kg | Closest Dose | 125mg | 250 mg | 500 mg |
|-----------------|--------------|-------|--------|--------|
| 20.0 - 22.9 | 625 | 1 | | 1 |
| 23.0 - 27.1 | 750 | | 1 | 1 |
| 27.2 - 31.3 | 875 | 3 | | 1 |
| 31.4 - 35.4 | 1000 | | | 2 |
| 35.5 - 39.6 | 1125 | 1 | | 2 |
| 39.7 - 43.8 | 1250 | | 1 | 2 |
| 43.9 - 47.9 | 1375 | 3 | | 2 |
| 48.0 - 52.1 | 1500 | | | 3 |
| 52.2 - 56.3 | 1625 | 1 | | 3 |
| 56.4 - 60.4 | 1750 | | 1 | 3 |
| 60.5 - 64.6 | 1875 | 3 | | 3 |
| 64.7 - 68.8 | 2000 | | | 4 |
| 68.9 - 72.9 | 2125 | 1 | | 4 |
| 73.0 - 77.1 | 2250 | | 1 | 4 |
| 77.2 - 81.3 | 2375 | 3 | | 4 |
| 81.4 - 85.4 | 2500 | | | 5 |
| 85.5 - 89.6 | 2625 | 1 | | 5 |
| 89.7 - 93.8 | 2750 | | 1 | 5 |
| 93.9 - 97.9 | 2875 | 3 | | 5 |
| 98.0 - 102.1 | 3000 | | | 6 |
| 102.2 - 106.3 | 3125 | 1 | | 6 |

| Pt Weight in Kg | Closest Dose | 125mg | 250 mg | 500 mg |

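### The creatinine rule in Protocol Section 6.4.4 has no entry for 25 mg/kg/day, and its re-escalation by doubling aims at an undefined initial dose that it cannot reach for prior doses of 15, 25 or 30

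*Protocol*

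**What the plan says.** **Reduction.** Under Protocol Section 6.4.4, a creatinine rise of at least 33% over baseline that is also above the upper limit of normal (ULN), seen on two consecutive occasions, triggers a reduction. The list has four lines. The first reads "15 mg/kg if the patient takes 30 mg/kg/day". The second brings those on 15 to 20 down to 10, and the third brings those on 10 down to 5. The last reads "study drug held if patient takes 5 mg/kg/day of deferasirox".

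**Re-escalation.** If creatinine keeps rising beyond the ULN after a reduction, interruption is recommended. Once creatinine is back below the ULN on two consecutive visits, "it is recommended to resume therapy at 5 mg/kg/day". After one month without recurrence, "study medication can be doubled at one month intervals in order to return to the initial dose".

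**Doses in use.** Section 6.1.1 starts everyone at 10 mg/kg/day and moves them at Week 4 to 10, 15 or 20 according to baseline LIC. From Week 24, patients with LIC above 15 mg Fe/g dw go up by 5 to 10 mg/kg/day. The ceiling is stated as: "The maximum dose of deferasirox throughout the study will be 30 mg/kg/day". The tablet tables run from 5 to 30 mg/kg/day in steps of 5 and include the one headed "Table 6-5 Deferasirox dosing table for 25 mg/kg/day".

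**Uncovered cases.** Section 6.4 sends an adjustment that its subsections do not cover to the sponsor as a written request. It also requires sponsor authorisation for adjustments made for reasons the section does not list. Section 6.1.1 separately lets the investigator reduce or interrupt for safety reasons at any time.

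**The concern.** Section 6.4.4 is the protocol's graded response to a confirmed creatinine rise. A rule of this kind should give an answer at every dose the protocol uses, and a route back should be able to arrive at its stated destination. Neither is assured here.

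The gap falls in a relevant part of the dose range. Section 1.2.1.2 describes creatinine increases as dose-dependent. It also reports that, in the earlier placebo-controlled NTDT trial, three patients in the 10 mg/kg/day group (3/55 = 5.5%, mean actual dose 11.5 mg/kg/day) had two consecutive rises of more than 33% that were above the ULN. The present study goes up to 30 mg/kg/day, and safety up to that dose is a stated secondary objective. If sites settle the gaps in their own ways, the same creatinine event can lead to different dosing at different centres. The creatinine-driven changes in the dose-change summaries of SAP Section 2.4.1 would then partly reflect local interpretation.

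**Working it through.** The documents give no statistical figure to reproduce on this point. The check lists the dose levels and sets the rules beside each other.

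**Inputs.** Dose levels 5, 10, 15, 20, 25, 30 (Tables 6-1 to 6-6). Planned steps and the maximum of 30 (Section 6.1.1). Reduction list, restart at 5, and doubling (Section 6.4.4).

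**Step 1: which planned doses can occur.** From 10, 15 or 20 at Week 4, with later steps of 5 or 10 up to 30, the reachable doses are 10, 15, 20, 25 and 30. For example, 20 + 5 = 25 and 20 + 10 = 30.

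**Step 2: doubling from 5.** The dose after k doublings is 5 × 2^k, which gives 5, 10, 20, 40 for k = 0, 1, 2, 3.

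**Step 3: compare level by level** (mg/kg/day).

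| Level | Entry in reduction list | Reached by doubling from 5? | First value in the sequence above the level |
|---|---|---|---|
| 5 | held | yes (restart dose) | – |
| 10 | to 5 | yes | – |
| 15 | to 10 | no | 20 (20/15 = 1.33) |
| 20 | to 10 | yes | – |
| 25 | none | no | 40 (40/25 = 1.60; above the maximum) |
| 30 | to 15 | no | 40 (40/30 = 1.33; above the maximum) |

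One of six levels has no reduction entry. Three of six cannot be reached by doubling.

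**Step 4: can the missing entry be inferred?** The listed reductions follow no single ratio: 15/30 = 0.50, 10/20 = 0.50 and 5/10 = 0.50, but 10/15 = 0.67. Halving 25 gives 12.5, for which there is no dosing table. The list does not settle the entry for 25.

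**Step 5: what is the initial dose?** The protocol does not define it.

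- *Dose before the event.* Section 6.4.4 provides for doubling at monthly intervals, in the plural. From 5, one doubling already gives 10, so repeated doubling implies a higher target. On this reading the rule works for 10 and 20. It passes over 15 (10, then 20). It leaves prior doses of 25 and 30 without a usable step after 20.
- *Starting dose of 10 mg/kg/day.* Sections 2.3 and 6.1 use the word initial, or initially, for that dose. Other sections use different words for the dose before an interruption: previous effective dose (6.1.1), last dose (6.4.7) and previous dose (6.4.9). On this reading a single doubling finishes the sequence, and Section 6.4.4 states no route back above 10.

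The 15 mg/kg/day case is not marginal: it is the Week 4 dose for every patient with baseline LIC above 7 and up to 15 mg Fe/g dw.

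**The case against.** A reader might infer that the protocol directs a step to 40 mg/kg/day. It does not. Doubling is permitted rather than required, its purpose is to return to an earlier dose, and Section 6.1.1 caps every dose at 30. What survives is narrower: after 20, doubling and the cap cannot both be followed, so the next step for prior doses of 25 or 30 is undefined.

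A reader might also infer that a patient on 25 with a confirmed rise is unprotected, or must wait for the sponsor's written reply. The documents do not support that either. Section 6.1.1 lets the investigator reduce or interrupt for safety at once. Section 6.4.4 calls for discontinuation at creatinine above twice the ULN or clearance below 40 mL/min, whatever the dose. Creatinine is also checked weekly for four weeks after each escalation. What remains is that Section 6.4 is unclear for this case, because the reason (creatinine) is listed but the dose level is not.

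It can be argued that initial dose simply means the 10 mg/kg/day start, in which case the doubling problem disappears. The wording elsewhere gives that reading some support, while the plural intervals point the other way. Either way the term needs defining.

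Finally, doubling applies only after an interruption, the documents do not say how many patients took 25 or 30, and no effect on the primary endpoint, the power or a planned test is shown. All of this stands and limits the weight of the point.

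**Conclusion.** The point holds as an internal inconsistency in a stated renal safety rule. The absence of an entry for 25 mg/kg/day depends on no assumption: the dose is reachable, tabulated and not listed. The failure of doubling to end at 15, 25 or 30 rests on reading the initial dose as the dose before the event, which the text favours but does not state. On the other reading, the fault is an undefined term with no stated route back above 10.

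The consequence is an incomplete rule and possibly different handling between sites. That such differences occurred is not shown, and their frequency cannot be estimated from the documents. The point deserves correction because the rule conflicts with the protocol's own dose levels and maximum. It does not call the primary analysis into question.

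**What to change.** Reconcile Section 6.4.4 with Section 6.1.1, Section 6.4 and Tables 6-1 to 6-6 so that:

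1. every dose level in use is covered by the reduction list;
2. the initial dose is defined;
3. the re-escalation sequence can end at that dose and stays within the stated maximum;
4. Section 6.4 says whether a listed reason at an unlisted dose level needs a written request, and how this fits with the investigator's freedom in Section 6.1.1 to reduce or interrupt.

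The values are for the sponsor's clinical team; none is proposed here. The cost is wording, mainly in one section, through the amendment route of Section 12.1. It needs no new visits, samples or analyses.

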6.4.5 Increased urinary proteinuria/creatinine ratio

Deferasirox must be temporarily discontinued if the urinary protein/creatinine ratio increases to > 1.0 (mg/mg) in two consecutive second-void urine samples separated by a period of at least 48 hours. Deferasirox can be resumed at the same dose once the urinary protein/creatinine ratio is ≤ 0.5 (mg/mg) in two consecutive urine samples, separated by a period of at least 48 hours. If proteinuria of this same magnitude recurs, deferasirox must be discontinued again and then resumed at 50% of the dose once the urinary protein/creatinine ratio is ≤ 0.5 (mg/mg) in two consecutive urine samples separated by a period of at least 48 hours. Dose adjustment will be based on central laboratory results.

In case of a single increase of the urinary protein/creatinine ratio, the assessment must be repeated in two weeks.

6.4.6 Stevens-Johnson syndrome

Severe skin reactions, including Stevens-Johnson syndrome (SJS), have been reported during Exjade therapy. If SJS is suspected, study treatment must be immediately discontinued and not be reintroduced.

6.4.7 Skin rash (other than SJS)

For skin rash of mild/moderate severity (defined as those causing minimal symptoms which require no or minimal supportive treatment), study drug should be continued without dose adjustment. The skin rash may resolve spontaneously without further intervention. If the rash

persists for >1 week, or worsens, treatment with study drug will be interrupted. After the rash resolves, study drug should be restarted. Resume deferasirox at 50% of the patient's dose. If the rash does not recur, increase back to 100% of the patient's dose after 2 weeks. If the rash recurs, contact Novartis.

For severe cases (defined as those causing distressing symptoms, particularly those which require the administration of systemic steroids for symptom relief) treatment with study drug must be stopped until resolution of the rash. If necessary, a brief course of oral steroids may be given. After the rash resolves, study drug should be restarted. Resume deferasirox at 50% of the patient's dose. If the rash does not recur, increase dose by 5 mg/kg increments every 2 weeks until 100% of the patient's last dose is achieved. If the rash recurs, study treatment may be discontinued if the investigator believes that it is in the best interest of the patient.

Novartis may be contacted by the investigator to discuss dosing options if the investigator so desires.

6.4.8 Gastrointestinal disturbances

Patients with gastrointestinal symptoms or patients who are unable to tolerate deferasirox may (in this order):

- In the first instance try changing the timing of administration from morning to evening (30 minutes before taking food), and in addition, try using an anti-diarrheal agent for 2 days in case of diarrhea.
- If the symptoms still continue, try administering the daily dose as a split dose b.i.d. after first contacting Novartis. Once the symptoms resolve, b.i.d should be switched to o.d.

6.4.9 Hepatic impairment

In patients who develop moderate hepatic impairment (Child-Pugh Class B) during the study, the study medication will be interrupted and patient monitored. If liver disease prognosis improves, study medication can be reintroduced at 10 mg/kg/day or 50% of previous dose, whichever is less. While monitoring continues, dose may be increased by 5 mg/kg/day increments every 2 weeks to a maximum of 50% of patient's previous dose if the investigator determines that dose increase is in the best interest of the patient. Study medication must be used with caution in such patients.

In patients who develop severe hepatic impairment (Child-Pugh Class C) during the study, study medication must be discontinued.

6.4.10 Elevated liver function tests

If there is a persistent and progressive increase in serum transaminase levels that cannot be attributed to other causes, deferasirox should be interrupted. Once the cause of the liver function test abnormalities has been identified or after a return to normal levels, cautious re-initiation of deferasirox treatment at a lower dose followed by gradual dose escalation may be considered. In cases of a second rise in serum transaminase levels, the investigator must contact Novartis.

